4. TREATMENTS

4.1. Treatments Administered

4.1.1. Screening Period

No study medication will be provided in the Screening Phase.

4.1.2. Placebo Lead-In Period

Patients will be required to complete a single blind placebo lead-in period. Patients will receive a matching placebo of Cannabidiol Oral Solution 40 mg/kg/day divided into twice daily dose with standard meal for 2 weeks.

4.1.3. Titration Period

At Visit 3 (Baseline), eligible patients will enter a 1-week Titration Period and will be randomized in a 1:1 ratio to receive Cannabidiol Oral Solution (40 mg/kg/day) or matching Placebo twice daily.

Titration will begin at 20 mg/kg/day divided into twice daily dose with standard meal for 3 days. If the 20 mg/kg/day dose of study medication has been well tolerated, patients will increase the dose of study medication to 30 mg/kg/day divided into twice daily doses with standard meal for 3 days. If the 30 mg/kg/day dose of study medication has been well-tolerated, patients will up titrate to the maximum dose of 40 mg/kg/day and start the 12-week Maintenance Period.

If the initial 20 mg/kg/day or the 30/mg/kg/day dose of study medication was NOT well-tolerated, patients will be discontinued from the study.

4.1.4. Maintenance Period

At Visit 4, patients will enter a 12-week Maintenance Period and continue taking Cannabidiol Oral Solution or matching placebo divided into twice daily dose with standard meal.

Patients may have their dose of study medication adjusted down by one dose level on one occasion at the discretion of the Investigator, or qualified designee. If the 40 mg/kg/day dose of study medication was NOT well tolerated, patients may have their dose of study medication adjusted to 30 mg/kg/day. If patients are unable to tolerate the 30 mg/kg/day dose of study medication, the drug will be discontinued and the patient will be withdrawn from the study.

4.1.5. Taper Period

Following the completion of the Maintenance Period (Visit 10), patients will have the option to continue treatment in an open-label long-term safety study. Patients who choose to enroll in the long-term safety study will not have a follow-up visit. Patients who do not choose to enroll in the long-term safety study will taper the dose of study medication according to the following schedule: 40 mg/kg/day dose will be reduced to 30 mg/kg/day for three days, then 30 mg/kg/day will be reduced to 20 mg/kg/day for three days and then discontinued; 30 mg/kg/day dose will be reduced to 20 mg/kg/day for three days and then discontinued.

4.1.6. Follow-Up Period

A follow-up visit call will occur within 2 weeks after study completion. No study medication will be provided during this time.

4.2. Identity of Investigational Product

The active pharmaceutical ingredient (API) in Cannabidiol Oral Solution is a synthetic, pharmaceutical grade CBD manufactured according to cGMP. It is an off-white to pale yellow resin or crystal substance that is soluble in several organic solvents with an acid dissociation constant (pKa) of 9.64. The solution is a clear, colorless to pale yellow-brown colored solution (CBD concentration of 100 mg/mL) filled into a 30 mL amber glass vial. More detailed information may be found in the IB.

4.3. Method of Assigning Patients to Treatment Groups

Following the 2-week Placebo Lead-In Period of the study, patients will be randomized in a 1:1 ratio, using a web-based randomization system. The randomization will be stratified according to growth hormone treatment (yes/no).

4.4. Selection and Timing of Dose for Each Patient

Patients will receive Cannabidiol Oral Solution or matching placebo twice daily with standard meal as described in [Section 4.1](#). The date and time of all investigational product administrations will be documented in the CRF.

4.5. Blinding and Unblinding Treatment Assignment

In the double-blind treatment period of the study, all patients and study personnel involved in the conduct of the study, including data management, will be blinded to treatment assignment with the exception of a specified unblinded statistical programmer from the sponsor or sponsor's representative who will have access to the randomization codes. The unblinded study personnel will not otherwise participate in study procedures or data analysis before unblinding of the study data to all study-related personnel.

Study personnel will endeavor to safeguard the integrity of the study blind to minimize bias in the conduct of the study. Treatment unblinding is discouraged if knowledge of the treatment assignment will not materially change the planned management of a medical emergency. Unblinding will be permitted in a medical emergency that requires immediate knowledge of the patient's treatment assignment. If a medical emergency occurs and unblinding is required, the site will contact IXRS for drug assignment. Unblinding should be discussed in advance with the sponsor, sponsor's representative, or medical monitor if possible. For emergency unblinding, study personnel will contact the sponsor or sponsor's representative. If the investigator is not able to discuss treatment unblinding in advance, the sponsor or sponsor's representative must be notified, or medical monitor as soon as possible about the unblinding incident without revealing the patient's treatment assignment. The investigator or designee must record the date and reason for study unblinding in the source document for that patient. In all cases that are not emergencies, the investigator must discuss the event with the sponsor, sponsor's representative, and/or medical monitor prior to unblinding the patient's treatment assignment.

If the treatment assignment is unblinded for an individual patient, study personnel will be notified of that patient's treatment assignment without unblinding of the treatment assignments for the remaining patients in the study. Thus, the overall study blind will not be compromised. If a patient's treatment assignment is unblinded, he or she may or may not be asked to withdraw from the study. The investigator will make this decision after consultation with the sponsor, sponsor's representative, or medical monitor.

4.6. Treatment Compliance

The prescribed dosage, timing, and mode of administration of Cannabidiol Oral Solution may not be changed unless a safety concern or toxicity is identified for a patient.

Patient compliance will be calculated during Placebo Lead-In Period. Patients taking too much or too little study medication should be re-educated on the proper use of study medication. Non-compliance (<80% or >100%) should be evaluated by the Investigator for the need to withdraw the patient. The Investigator should discuss the case with the Medical Monitor.

4.7. Permitted and Prohibited Therapies

4.7.1. Permitted Therapies

Any medications (other than those excluded by the protocol, see [Section 4.7.2](#)) that the Investigator considers necessary for a patient's welfare and will not interfere with the investigational product may be given at the Investigator's discretion.

4.7.2. Prohibited Therapies

During the Screening, Placebo Lead-In, Titration, Treatment, and Follow-up Periods, patients are not to receive the following:

- Any cannabinoids other than study medication (CBD, Δ^9 -THC, hemp oil, Realm Oil or marijuana).
- Felbamate.
- Use of weight loss agents or drugs known to affect appetite (including glucagon-like peptide-1[GLP-1] analogs).
- Any other investigational drug or investigational device.
- Medication that are strong inhibitors/inducers/ sensitive substrates with a narrow therapeutic index for P450 3A4 (CYP3A4), CYP2D6, CYP3A4-, or CYP2D6.

Although they are not prohibited, patients taking concomitant medications may require that the patient is monitored with special care to identify any AEs arising due to the potential for altered drug metabolism.

4.8. Treatment After End of Study

After completion of the study, patients will be offered the chance to enroll into an open-label, long-term safety study. Patients who choose to enroll in the long-term safety study will not have a follow-up visit. Patients who do not choose to enroll in the long-term safety study will be tapered off study medication and complete a follow-up visit approximately 2 weeks after study completion.

5. STUDY DRUG MATERIALS AND MANAGEMENT

5.1. Labeling and Packaging

5.1.1. Labeling

The labels for the investigational product will contain all information according to regulatory requirements.

5.1.2. Packaging

A description of the drug product may be found in [Table 3](#). The investigational product will be supplied in 30 mL containers of a 100 mg/mL strength (i.e., 3000 mg per container).

Table 3: Description of Drug Product

Non-proprietary or common name of drug product	Cannabidiol Oral Solution, 100 mg/mL
Dosage form	Oral solution
Strength	100 mg/mL

Please refer to Cannabidiol Oral Solution IB for additional information on the drug formulation.

The investigational product will be clearly marked according to FDA and/or ICH requirements regarding use for clinical study investigation only and will be labeled with the investigational product name, study reference number, storage conditions, and expiry date. It is the responsibility of the Investigator to ensure that accurate accountability records are maintained throughout the study. Study center staff will dispense the investigational product according to the handling instructions.

5.2. Dispensing and Storage

Investigational product will be stored at controlled room temperature (20 to 25 degrees Celsius, 68 to 77 degrees Fahrenheit) at the study centers.

Cannabis and its constituents (including CBD) are Schedule I controlled substances and patient to all applicable local and federal laws and regulations regarding these products. This includes security provisions for storing the controlled substances and for dispensing in a manner to prevent diversion. Additionally, the Sponsor or Investigator must provide a statement of the quantity to be manufactured and the sources of the chemicals to be used or the substance.

The DEA regulations detail specific security requirements for storage of the investigational product. Licensed practitioners must store controlled substances in a “securely locked, substantially constructed cabinet” and must notify the DEA of the theft or significant loss of any controlled substances within one business day of discovering such loss or theft. Furthermore, all practitioners are prohibited from hiring employees who have been convicted of a drug-related felony or who have had a DEA registration denied or revoked.

Investigators are responsible for ensuring that all applicable licensures are in place and storage conditions are appropriate.

Doses of Cannabidiol Oral Solution will be dispensed from the Schedule I-licensed study center.

The study centers are required to provide complete information, including case report forms (CRFs) and final outcomes, on all instances of addiction, abuse, misuse, overdose, drug diversion/drug accountability, discrepancies in amount of the clinical supplies of the investigational product, noncompliance, protocol violations, lack of efficacy, individuals lost to follow-up, and any other reasons why patients dropped out of the study.

5.3. Drug Supply and Accountability

The Investigator, a member of the investigational staff, or a hospital pharmacist must maintain an adequate record of the receipt and distribution of all study medication using the Drug Accountability Form. These forms must be available for inspection at any time.

All supplies of Cannabidiol Oral Solution should be accounted for at the termination of the study and a written explanation provided for discrepancies. All unused supplies and packaging materials are to be inventoried and returned to the Sponsor or a designee by the Investigator. The Investigator is not permitted to return or destroy unused clinical drug supplies or packaging materials unless authorized by the Sponsor or a designee.

If the study is terminated, discontinued, suspended, or completed, all unused supplies of the investigational product may be destroyed by via the use of a third-party vendor or be returned to the Sponsor or a designee after the final drug accountability check has been performed. A certificate of destruction will be provided to the Sponsor.

All regulations issued by the DEA concerning the accountability of Schedule I medications will be followed (e.g., prevention of diversion).

6. STUDY ASSESSMENTS

6.1. Efficacy Assessments

The efficacy assessments to be performed throughout the study are:

6.1.1. Body Weight Measurements

Body weight measurements will be obtained in the fasted, voided state at each Visit (Screening, Placebo Lead-In, Baseline, Week 1, Week 3, Week 5, Week 7, Week 9, Week 11, and Study Completion/Early Withdrawal (Week 13).

6.1.2. Hyperphagia Questionnaire-Clinical Trial (HQ-CT)

The HQ-CT will be completed at each Visit (Screening, Placebo Lead-In, Baseline, Week 1, Week 3, Week 5, Week 7, Week 9, Week 11, and Study Completion/Early Withdrawal (Week 13). The questionnaire assesses food-related problem behaviors and consists of three factors: Hyperphagic Drive (internal consistency 0.76), Hyperphagic Behavior (internal consistency 0.80) and Hyperphagic Severity (internal consistency 0.60). It is a 13-item parent completed questionnaire (Fehnel et al., 2015).

6.1.3. Three Factor Eating Questionnaire (TFEQ-R18)

The TFEQ-R18 will be completed at Visits 3, 5, 8, and 10 (Baseline, Week 3, Week 9, and Study Completion/Early Withdrawal [Week 13], respectively). The TFEQ-R18 consists of 18 items designed to assess three dimensions of eating behavior: Cognitive Restraint, Uncontrolled Eating, and Emotional Eating (Karlsson et al., 2000).

6.1.4. Quality of Life (PROMIS Life Satisfaction and Positive Affect)

The PROMIS Life Satisfaction and Positive Affect pediatric short-form questionnaires will be completed at Visits 3, 5, 8, and 10 (Baseline, Week 3, Week 9, and Study Completion/Early Withdrawal [Week 13], respectively). These questionnaires are designed to determine the patient's own judgement concerning their satisfaction with their life currently and are appropriate for children and adolescents.

6.1.5. Physical Activity (PROMIS Physical Activity and Fatigue)

The PROMIS Physical Activity and Fatigue pediatric short-form questionnaires will be completed at Visits 3, 5, 8, and 10 (Baseline, Week 3, Week 9, and Study Completion/Early Withdrawal [Week 13], respectively). These questionnaires are designed to determine the patient's physical activity and are appropriate for children and adolescents.

6.1.6. Dual Energy X-ray Absorptiometry (DEXA) Scan

Changes in body composition (total fat/lean body mass/bone mineral content) will be measured at Visit 3 and Visit 10 (Baseline and Study Completion/Early Withdrawal [Week 13], respectively). Lean body mass (LBM) will be calculated as fat free mass (FFM) minus bone mineral content. Fat percentage will be expressed as percentage of total body mass.

6.1.7. Patient Global Impression of Severity (PGI-S)

The Patient Global Impression of Severity will be completed at Visit 3 (Baseline). The questionnaire consists of 1-item designed to assess the patient's impression of disease severity.

6.1.8. Patient Global Impression of Change (PGI-C)

The Patient Global Impression of Change will be completed at Visit 5, 8, and 10 (Week 3, Week 9, and Study Completion/Early Withdrawal [Week 13], respectively). The questionnaire consists of one item designed to assess the patient's impression of change.

6.2. Safety Assessments

Safety assessments for all patients will include medical history, physical examination, vital signs (seated blood pressure, pulse rate, temperature, and respiration rate), clinical laboratory testing (including CBC), 12-lead ECG, urine drug screen (including THC), prior medication history, concomitant medication, and AE assessments.

6.2.1. Demographics and Medical History

Each potential study participant will have the following assessments by the Investigator or designee within 2 weeks prior to the Placebo Lead-in Period: medical history and demographic data, including sex, age, race, ethnicity, body weight (kg), height (cm), and BMI (kg/m²).

6.2.2. Physical Examinations

A physical examination will be conducted for every patient at every visit: Screening (Visit 1), Placebo Lead-In (Visit 2), Baseline (Visit 3), Titration Period (Visit 4), Maintenance Period (Visits 5, 6, 7, 8, 9), and Study Completion/Early Withdrawal (Visit 10) Visits. The examination will include evaluation of ears, eyes, nose, and throat (EENT), heart, peripheral vasculature, lungs, musculoskeletal system, abdomen, neurologic function, endocrine system, and skin.

6.2.3. Vital Signs

Vital signs (seated blood pressure, pulse rate, temperature and respiration rate) will be measured at every visit: Screening (Visit 1), Placebo Lead-In (Visit 2), Baseline (Visit 3), Titration Period (Visit 4), Maintenance Period (Visits 5, 6, 7, 8, 9), and Study Completion/Early Withdrawal (Visit 10) Visits.

Additional vital sign measurements may be performed as deemed medically necessary by research personnel.

6.2.4. Electrocardiograms

A resting 12-lead ECG will be conducted for every patient at the Screening (Visit 1), Maintenance Period (Visits 6, 8), and Study Completion/Early Withdrawal (Visit 10) Visits.

6.2.5. Clinical Laboratory Assessments

6.2.5.1. Hematology

Blood samples for the following hematology assessments will be collected at the Screening (Visit 1), and Study Completion/Early Withdrawal (Visit 10) Visits: hemoglobin, hematocrit, total and differential leukocyte count, red blood cell (RBC), and platelet count.

6.2.5.2. A sample for complete blood count (CBC) will be collected at Week 3 (Visit 5).Chemistry

Blood samples for the following serum chemistry assessments will be collected at the Screening (Visit 1), and Study Completion/Early Withdrawal (Visit 10) Visits: albumin, blood urea nitrogen (BUN), creatinine, total bilirubin, alkaline phosphatase (ALP), aspartate transaminase (AST), alanine transaminase (ALT), sodium (Na⁺), potassium (K⁺), chloride (Cl⁻), lactate dehydrogenase (LDH), uric acid, glucose, and calcium.

6.2.5.3. Urinalysis

Urine samples for the following assessments will be collected at the Screening (Visit 1) and Study Completion/Early Withdrawal (Visit 10) Visits: pH, specific gravity, protein, glucose, ketones, bilirubin, blood, nitrite, leukocyte esterase, and urobilinogen. If protein, occult blood, nitrite, or leukocyte esterase values are out of range a microscopic examination will be performed.

6.2.5.4. Pregnancy Screen (Female Patients)

A urine dipstick pregnancy test will be performed on all female patients at the Screening (Visit 1) and Study Completion/Early Withdrawal (Visit 10) Visits. A positive pregnancy test will result in screening failure or the patient being withdrawn from the study.

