Exploratory analyses of dose (exposure)-response relationship will be performed. Further population PK approach may be used for PK parameter calculations, as appropriate.

Missing Data

For efficacy measures, missing data points may be imputed using Jump to Reference as a conservative method. For safety data, there will be no imputation of missing data, and the safety assessments will be conducted based on the observed data.

Table 1: Schedule of Assessments

Assessment	SCREENING (2 Weeks)	SINGLE BLIND PLACEBO LEAD-IN (2 Weeks)	DOUBLE-BLIND TREATMENT PHASE									FOLLOW -UP PERIOD ^b (2 Week)
			TITRATION PERIOD ^a (1 Week)			MAINTENANCE PERIOD (12 Weeks)						
Visit Number	1	2	3 Baseline	Call/ Email	4	5	6	7	8	9	10 Study Completion / Early Withdrawal	11
Study Time Point	Week -4 to -2	Week -2	Day 1	Day 3 & 6	Day 7	Week 3	Week 5	Week 7	Week 9	Week 11	Week 13	Week 15
Visit Window (Days)	±3	±3	±3	0	0	±3	±3	±3	±3	±3	±3	±3
Informed consent/assent (if appropriate)	X											
Medical/surgical history	X											
Demographics	X											
Review of inclusion and exclusion criteria	X											
Randomization			X									
Physical exam	X	X	X		X	X	X	X	X	X	X	
Record vital signs	X	X	X		X	X	X	X	X	X	X	
Resting 12-lead ECG	X						X		X		X	
Clinical laboratory tests ^d	X					X					X	
Urinalysis	X										X	

Assessment	SCREENING (2 Weeks)	SINGLE BLIND PLACEBO LEAD-IN (2 Weeks)	DOUBLE-BLIND TREATMENT PHASE									FOLLOW -UP PERIOD ^b (2 Week)
			TITRATION PERIOD ^a (1 Week)			MAINTENANCE PERIOD (12 Weeks)						
Visit Number	1	2	3 Baseline	Call/ Email	4	5	6	7	8	9	10 Study Completion / Early Withdrawal	11
Study Time Point	Week -4 to -2	Week -2	Day 1	Day 3 & 6	Day 7	Week 3	Week 5	Week 7	Week 9	Week 11	Week 13	Week 15
Visit Window (Days)	±3	±3	±3	0	0	±3	±3	±3	±3	±3	±3	±3
Urine dipstick for females of childbearing potential only	X										X	
Urine drug screen (drugs of abuse including THC)	X											
Dosing with Study Medication		X	X	X	X	X	X	X	X	X	X	
Dispense/Review/Collect study medication		X	X	X	X	X	X	X	X	X	X	X
Hyperphagia Questionnaire for Clinical Trial (HQ-CT)	X	X	X		X	X	X	X	X	X	X	
Weight	X	X	X		X	X	X	X	X	X	X	
Three Factor Eating Questionnaire (TFEQ- R18)			X			X			X		X	
PROMIS Life Satisfaction and Positive Affect pediatric short- form questionnaires			X			X			X		X	

Assessment	SCREENING (2 Weeks)	SINGLE BLIND PLACEBO LEAD-IN (2 Weeks)	DOUBLE-BLIND TREATMENT PHASE									FOLLOW -UP PERIOD ^b (2 Week)

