3.2. Patient Selection

3.2.1. Inclusion Criteria

All patients must satisfy the following criteria to be considered for study participation:

1. Patient and/or parent(s)/caregiver(s) fully comprehend the informed consent form (ICF) and assent form, understand all study procedures, and can communicate satisfactorily with the investigator and study coordinator, in accordance with applicable laws, regulations, and local requirements.
2. Males and females from 8-17 years of age, inclusive.
3. Genetically confirmed diagnosis of Prader-Willi Syndrome using standard DNA methylation test or fluorescent *in situ* hybridization. Documentation of genetically confirmed diagnosis of Prader-Willi Syndrome is acceptable.
4. A score of ≥ 10 on the HQ-CT.
5. A caregiver is available to complete the HQ-CT.
6. If female, is either not of childbearing potential (defined as premenarchal or surgically sterile [bilateral tubal ligation, bilateral oophorectomy, or hysterectomy]) or practicing one of the following medically acceptable methods of birth control:
 - a. Hormonal methods such as oral, implantable, injectable, vaginal ring, or transdermal contraceptives for a minimum of 1 full cycle (based on the patient's usual menstrual cycle period) before study drug administration.
 - b. Total abstinence from sexual intercourse since the last menses before study drug administration.
 - c. Intrauterine device.
 - d. Double-barrier method (condoms, sponge, or diaphragm with spermicidal jellies or cream).
7. Adequate renal function, defined as serum creatinine $\leq 1.5 \times$ upper limit of normal (ULN) and urine protein/creatinine ratio < 0.2 .
8. Adequate hepatic function, defined as total bilirubin $\leq 1.5 \times$ ULN and aspartate aminotransferase (AST) and Alanine aminotransferase (ALT) levels $\leq 3 \times$ ULN.
9. Growth hormone treatment will be permitted if doses have been stable for at least 1 month prior to screening.
10. Psychotropic treatment will be permitted and should be stable at least 6 weeks prior to screening.
11. Any other treatment including thyroid hormones should be stable for at least 6 weeks prior to screening.

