3.2.2. Exclusion Criteria

Patients will be excluded for any of the following:

1. Known use of cannabis or cannabinoid-containing products for 4 weeks prior to baseline.
2. History of chronic liver disease, such as cirrhosis or chronic hepatitis due to any cause, or suspected alcohol abuse.
3. Use of weight loss agents or drugs known to affect appetite (including glucagon-like peptide-1[GLP-1] analogs) within 2 months prior to screening.
4. Uncontrolled Type I and Type II diabetes.
5. Currently taking concomitant medications that are strong cytochrome P450 3A4 (CYP3A4) or CYP2D6 inhibitors; or inducers of CYP3A4- or CYP2D6-sensitive substrates with a narrow therapeutic index.
6. Co-morbid condition or disease (such as respiratory disease, heart disease, or psychiatric disorder) diagnosed less than 1 month prior to screening.
7. History or presence of gastrointestinal or any other condition known to interfere with the absorption, distribution, metabolism or excretion of drugs as determined by the Investigator.
8. Patients who have participated in any other trials involving an investigational product or device within 30 days of screening or longer as required by local regulations.
9. Clinically significant abnormalities on ECG at screening or other evidence of heart disease as determined by the Investigator.
10. Has screening systolic blood pressure ≥ 160 mm Hg and diastolic blood pressure > 100 mm Hg (may be repeated one additional time after 5 minutes' rest to verify). Patients with hypertensive levels lower than those specified may be excluded at the Investigator's discretion if deemed to be in the best interest of the patient.
11. Currently taking felbamate.
12. Uncontrolled sleep apnea.
13. Pregnant or lactating female.
14. History of hypersensitivity to drugs with a similar chemical structure or class as CBD.
15. Unwillingness or inability to follow the procedures outlined in the protocol.
16. Patient judged by the investigator or sponsor (or designee) as unable to comply with the treatment protocol, including appropriate supportive care, follow-up and research tests.
17. Positive drug screen, including THC, at time of screening.
18. Creatinine clearance test of < 30 mL/min.

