7.2. Placebo Lead-In Period

7.2.1. Visit 2 (Week -2)

Patients who complete all Screening assessments and meet the study entry criteria will be assigned to the Placebo Lead-In Period. The following procedures and assessments will be performed at Visit 2:

- Perform a complete physical examination.
- Record vital signs (seated blood pressure, pulse rate, temperature, and respiration rate).
- Dispense study medication.
- Record weight.
- Complete the HQ-CT.
- Review concomitant medications.

- Review AEs.

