7.3. Titration Period

7.3.1. Baseline (Visit 3, Day 1)

At Visit 3 (Baseline), eligible patients will be randomized and enter a 1 week Titration Period.

The following procedures and assessments will be performed at Baseline (Visit 3):

- Randomization.
- Perform a complete physical examination.
- Record vital signs (seated blood pressure, pulse rate, temperature, and respiration rate).
- Collect/review/dispense study medication.
- Record weight.
- Complete the HQ-CT.
- Complete the TFEQ-R18.
- Complete the PROMIS Life Satisfaction and Positive Affect questionnaires.
- Complete the PROMIS Physical Activity and Fatigue questionnaires.
- Complete PGI-S.
- Perform DEXA scan.
- Complete the C-SSRS.
- Take PK sample blood draw.
- Review concomitant medications.
- Review AEs.

Titration will begin at 20 mg/kg/day divided into twice daily dose with standard meal for 3 days. If the 20 mg/kg/day dose of study medication has been well tolerated, patient will increase the dose of study medication by 1 dose level to 30 mg/kg/day divided into twice daily dose with standard meal for 3 days. If the 30 mg/kg/day dose of study medication has been well-tolerated, patient will up titrate to the maximum dose of 40 mg/kg/day and start the 12-week Maintenance Period.

If the initial 20 mg/kg/day or the 30/mg/kg/day doses of study medication were NOT well-tolerated, the drug will be discontinued and the patient withdrawn from the study.

The Investigator or designee will call on Day 3 and Day 6 to determine if the patient's dose may be titrated to the next dose level.

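### No pregnancy test is scheduled at Visit 3, so the only test result available at the first double-blind dose is nominally 14 to 28 days old.

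*Protocol*

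**What the plan says.** Exclusion 13 in Protocol 3.2.2 reads "Pregnant or lactating female". Section 6.2.5.4 sets the testing schedule: "A urine dipstick pregnancy test will be performed on all female patients at the Screening (Visit 1) and Study Completion/Early Withdrawal (Visit 10) Visits". It adds that a positive test leads to screen failure or withdrawal. The Table 1 row "Urine dipstick for females of childbearing potential only" is marked at Visits 1 and 10 only, and SAP Appendix A repeats it. Sections 7.1 and 7.4.2 list the test at those two visits. SAP 7.7.3.3 mentions Screening only.

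Two site visits lie between Screening and the first active dose. For Visit 2, section 7.2.1 says: "Patients who complete all Screening assessments and meet the study entry criteria will be assigned to the Placebo Lead-In Period". For Visit 3, section 7.3.1 says: "At Visit 3 (Baseline), eligible patients will be randomized and enter a 1 week Titration Period". Neither visit's procedure list includes a pregnancy test. The Table 1 row "Review of inclusion and exclusion criteria" is marked at Visit 1 only.

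**The concern.** The plan treats pregnancy as disqualifying: it is an exclusion, a reason for discontinuation (3.3), and grounds for screen failure or withdrawal when a test is positive. The test is nevertheless not placed where active exposure begins. A patient who conceives after Visit 1, or whose pregnancy is too early to detect there, can pass through the two-week placebo lead-in, be randomized, and start titration from 20 to 40 mg/kg/day with no scheduled test in between. No scheduled step re-checks exclusion 13 at randomization either.

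What is at stake is an avoidable exposure of a pregnant minor to active drug. Efficacy inference is not at issue. A pregnancy found before randomization also keeps the patient out of the ITT population, which is all randomized patients (Protocol 8.5, SAP 5.1). The same pregnancy found later becomes a withdrawal after randomization.

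**Working it through.** **Inputs from the documents**

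- Visit 1: Week -4 to -2, window ±3 days (Table 1).
- Screening: within 2 weeks before the lead-in starts (7.1). Lead-in: 2 weeks (3.1).
- Day 1: date of the first double-blind dose. Earlier days are counted as assessment date minus Day 1 date (SAP 6.1).
- Visit 3: Day 1, window ±3 days. Visit 10: Week 13 (Table 1).
- Planned number randomized: about 66 (8.4).

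**Age of the test result at the first double-blind dose**

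1. From the period lengths: 0 to 14 days of screening plus 14 days of lead-in gives 14 to 28 days. This reproduces Table 1's Week -4 to -2 (2 × 7 = 14; 4 × 7 = 28).
2. With the Visit 1 window alone, Day 1 being fixed as the first dose: 14 − 3 = 11 to 28 + 3 = 31 days.
3. If the Visit 3 window is also applied: 11 − 3 = 8 to 31 + 3 = 34 days.
4. With a dipstick at Visit 3 before dosing: 0 days.

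**Interval between the two scheduled tests**

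Visit 10 is about 13 × 7 = 91 days after Day 1, so Visit 1 to Visit 10 is 14 + 91 = 105 to 28 + 91 = 119 days. The part before dosing is 14/105 = 13% to 28/119 = 24% of that.

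**Tests added**

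The documents give neither the sex split nor menarchal status, so these are assumptions.

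| Assumption | Low | High |
|---|---|---|
| 40% to 60% female, all of childbearing potential | 0.40 × 66 = 26.4 | 0.60 × 66 = 39.6 |
| 25% to 100% of those of childbearing potential | 0.25 × 26.4 = 6.6 | 1.00 × 39.6 = 39.6 |
| False positives at 0.5% to 2% per test | 6.6 × 0.005 = 0.03 | 39.6 × 0.02 = 0.79 |

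This gives about 26 to 40 tests if every female is of childbearing potential, about 7 to 40 over the wider range, and fewer than one expected false positive in the trial.

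**The case against.** The strongest reply is that other safeguards operate at dosing and the risk is small.

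- Inclusion 6 requires non-childbearing status, contraception or abstinence. Items 6a and 6b are tied to dosing rather than to Visit 1; 6b reads "Total abstinence from sexual intercourse since the last menses before study drug administration".
- Section 4.1.3 says "At Visit 3 (Baseline), eligible patients will enter a 1-week Titration Period and will be randomized in a 1:1 ratio", which implies that eligibility still holds at Visit 3.
- Visits 2 and 3 include a physical examination, adverse event review and concomitant medication review.
- Patients are 8 to 17 years old, some girls will be premenarchal, and section 1.4 describes hypogonadism.
- The documents show no embryo-fetal risk. Section 1.2.1 mentions effects on spermatogenesis and follicle-stimulating hormone, then defers to the Investigator's Brochure.
- A Visit 3 dipstick can itself miss a very recent conception, and it leaves about 90 days of treatment without a scheduled test.

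Most of this stands as a limit on importance. Conception in the window is unlikely, and a result aged 0 days does not mean that no conception goes undetected. The on-treatment interval is the longer one; it is outside this point and lends it no weight.

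None of these safeguards, however, supplies a test result or a scheduled re-check of exclusion 13 before active dosing. The dosing anchor in 6a and 6b is also loose, because study medication is first dispensed at Visit 2 as placebo, so it can be read as preceding Visit 3. The sponsor evidently does not regard age and hypogonadism as sufficient, since it requires both contraception and testing.

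**Conclusion.** The point holds. No pregnancy test is scheduled between Visit 1 and the first double-blind dose, and the Screening result is then nominally 14 to 28 days old (11 to 31 with the Visit 1 window; 8 to 34 only if the Visit 3 window is added). These figures rest on the documents alone.

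The number of patients affected cannot be estimated and is probably very small, and the primary analysis is unaffected. The case for change is that a cheap check in minors belongs at the last point where a first exposure to active drug can still be prevented. The sponsor should make it, although it is not a critical defect. Confidence in the schedule facts is high; the test counts and false-positive figures are illustrative because their inputs are assumed.

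**What to change.** Add the urine dipstick already in use at Visit 3, before randomization and dosing, for females of childbearing potential, and reassess that status at Visit 3, since menarche can occur after Screening. Amend Table 1, 6.2.5.4, 7.3.1 and SAP Appendix A. State that a patient with a positive result is neither randomized nor dosed. SAP 7.2 already has a disposition category for patients screened but not randomized, so no new reporting category is needed.

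As an editorial matter only, align 6.2.5.4 and SAP 7.7.3.3, which refer to all females, with Table 1, 7.1, 7.4.2 and Appendix A, which limit testing to those of childbearing potential. SAP 7.7.3.3 should also name every test visit.

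The cost is one urine collection and reading per tested patient at an existing visit. Table 1 schedules no urine sample at Visit 3, so the collection is new. On the stated assumptions this is at most about 26 to 40 tests among 66 patients; replaced patients, or patients who reach Visit 3 but are not randomized, would add a few. The downsides are a short wait before randomization and a rare false positive that needs a repeat test.
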